## 13.2. Analysis of Outcomes

A separate Statistical Analysis Plan (SAP) will be produced and will provide a more comprehensive description of the planned statistical analyses. A brief outline of these analyses is given below.

The primary comparison groups will be composed of those randomised to planned ABA-feed intervention (plus usual feeding care) versus those randomised to usual feeding care. In the first instance, all analyses will be based on the intention to treat (ITT) principle, i.e. all participants will be analysed in the intervention group to which they were randomised irrespective of adherence or other protocol deviation apart from pregnancy loss, stillbirth or infant death prior to an outcome assessment, where participants will be excluded from the analysis of outcomes after the date of loss/death. A sensitivity analysis will be performed on the per-protocol population to assess the robustness of the finding.

For all outcome measures, appropriate summary statistics and differences between groups (e.g. mean differences, relative risks) will be presented, with 95% confidence intervals (CI) and p-values from two-sided tests also provided, unless otherwise specified in section 8.2. Intervention effects will be adjusted for the minimisation variables (age group and site) where possible, and baseline value for outcomes where this was measured. Clustering by IFH will be accounted for in the model. No adjustment for multiple comparisons will be made.

## 13.2.1. Primary Outcome

The primary outcome (i.e. baby receiving any breast milk' at 8-weeks post birth) is a binary outcome (i.e. yes/no) and will be analysed using a mixed effects log binomial regression model, adjusting for the intervention group and the minimisation variables listed in Section 6.2 (age group and site). Age (as a continuous variable) will be treated as a fixed effect and site and IFH will be treated as random effects. The treatment effect will be expressed as an

adjusted risk ratio and a risk difference with associated 95% CIs. If the model does not converge, alternative models will be considered, e.g. log Poisson regression models with robust variance estimation. The p-value from the associated model will be produced and used to determine statistical significance of the estimated treatment group parameter.

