# 6.3. Randomisation

After eligibility has been confirmed and informed consent has been received (as outlined in section 5) and the baseline questionnaire completed, the woman can be randomised into the trial.

Randomisation will be provided by a secure online randomisation system at the Birmingham Clinical Trial Unit (BCTU). Unique login usernames and passwords will be provided to those who wish to use the online system and who have been delegated the role of randomising participants into the study as detailed on the ABA-feed Trial Training Log and ABA-feed Delegation Log. The online randomisation system will be available 24 hours a day, seven days a week, apart from short periods of scheduled maintenance. A back-up telephone toll-free randomisation service ([name]) is available Monday to Friday, 09:00 to 17:00 UK time, except for bank holidays, government guided closures and University of Birmingham closed days.

An Eligibility/Randomisation Form will be provided to investigators and will be used to collate the necessary information prior to randomisation. If any data items are missing, randomisation will be stopped, but can be restarted once the information is available. Only when all eligibility criteria and baseline data items have been provided will a Trial Number be allocated.

The ABA-feed trial is individually randomised. We have inflated the sample size in the intervention group only to account for the effect of potential clustering by feeding helper in the analysis, so randomisation would allocate more women to the intervention arm than control (1606 vs 1124).

Women will be randomised by computer at the level of the individual participant in a 1.43:1 ratio to either ABA-Feed or the control group. A minimisation algorithm will be used within the online randomisation system to ensure balance in the treatment allocation over the following variables:

- site
- woman's age (<25, ≥25)

A 'random element' will be included in the minimisation algorithm, so that each woman has a probability (unspecified here), of being randomised to the opposite treatment that they would have otherwise received. Full details of the randomisation specification will be stored in a confidential document at BCTU.

Following randomisation, a confirmatory e-mail will be sent to the research team at the relevant Hub and the ABA-feed Trial Office.

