#### 8.3.1. Baseline data

Women who are recruited in-person will complete a paper version of the baseline questionnaire, it will be entered into the study database by the recruiting centre/Hub centre staff or Trial office. Women recruited remotely will complete the baseline questionnaire online via a web-link emailed to them by the researcher at recruiting centre/Hub. If they do not have internet access a paper version will be posted to them to be returned with pre-paid addressed envelope to the recruiting centre/hub research staff or Trial office.

At recruitment women will be asked to provide demographic characteristics (date of birth, ethnicity, highest level of qualification, relationship status, postcode (for calculation of Index of Multiple Deprivation quintile), work status), how they were fed as a baby, thoughts about how they might feed their baby, MOS social support scale, GAD-7 and EuroQol EQ-5D-5L.

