# **13. STATISTICAL CONSIDERATIONS**

## 13.1. Sample Size

Assuming 90% power and a 2-sided 5% significance level, with a control group rate of 44% for the primary outcome (95% CI 30.0% to 58.7%; from the ABA feasibility data), a sample size of 2,136 women (1,068 per group) would be required to detect a risk ratio of 1.16 (i.e. an increase of 7% from 44% to 51%), considered to be a clinically meaningful increase. Since the intervention will be delivered by IFHs, there is a potential for clustering of outcomes by IFH. To allow for this potential clustering effect the sample size for the intervention arm requires inflation, assuming an intra-cluster correlation coefficient of 0.039 taken from ABA feasibility data and given that each IFH will support about 12 women. The sample size required for the intervention arm is thus 1,526, giving a total sample size of 2,594 (1526 intervention + 1068 control). Allowing for a 5% loss to follow-up (as in the ABA feasibility study), a total of 2,730 (1,606 intervention and 1,124 control arm) women would be required (2594/0.95).

Assuming 80% power, the sample size of 2,730 would allow the detection of a risk ratio of 1.14 equivalent to a 6% absolute increase.

With an average 12 women/IFH we need to train 134 peer supporters (1606/12).

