## 13.3.Subgroup Analyses

Subgroup analyses will be undertaken on: (i) variables used in the minimisation algorithm other than site (i.e. age); and (ii) other variables of prognostic importance to explore the effect of context, pre-specified as feeding intentions, mother's education, Index of Multiple Deprivation (IMD) and relationship status. Subgroup analyses will be limited to the primary outcome only. Tests for statistical heterogeneity (e.g. by including the treatment group by subgroup interaction parameter in the regression model) will be presented alongside the effect estimate and 95% CI within subgroups. The results of subgroup analyses will be treated with caution and will be used for the purposes of hypothesis generation only.

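### The primary model leaves out baseline feeding intention, which the protocol calls prognostic and collects before randomisation: a modest, avoidable loss of precision, not a bias

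*Protocol*

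**What the plan says.** Protocol section 13.2.1 sets the primary model as a mixed effects log-binomial regression, "adjusting for the intervention group and the minimisation variables listed in Section 6.2 (age group and site". Age enters as a fixed effect; site and IFH enter as random effects.

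Section 13.2 gives the general rule: adjust for the minimisation variables and, where one was measured, for the outcome's own baseline value.

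Section 13.3 plans subgroup analyses of the primary outcome on age and on "other variables of prognostic importance to explore the effect of context, pre-specified as feeding intentions", followed by mother's education, deprivation index and relationship status. These analyses are for hypothesis generation only.

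Intention is available for this use. The recruitment data include "thoughts about how they might feed their baby" (section 8.3.1; also the feeding-plans row of Table 1). Section 6.3 states: "Only when all eligibility criteria and baseline data items have been provided will a Trial Number be allocated". Minimisation, also in section 6.3, uses site and age group only.

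**The concern.** The trial enrols first-time mothers whatever their feeding plans, so intention can be expected to vary between participants. The protocol itself regards it as prognostic. Yet intention is neither balanced by the allocation nor adjusted for in the primary model.

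The general rule in section 13.2 does not bring it in. Breastfeeding has no value before birth, so the primary outcome has no baseline measurement to adjust for. GAD-7, EQ-5D-5L and social support do have one. Intention is the nearest counterpart that the trial collects.

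Two things are at stake. The confidence interval for the primary result is wider than the collected data allow, by an amount that depends on how prognostic intention is. And if the arms differ by chance in intention, the primary estimate carries that difference uncorrected.

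**Working it through.** **Inputs** (protocol section 13.1)
- Error rates and control rate: "Assuming 90% power and a 2-sided 5% significance level, with a control group rate of 44% for the primary outcome".
- Target effect: "detect a risk ratio of 1.16 (i.e. an increase of 7% from 44% to 51" per cent.
- Clustering in the intervention arm: "assuming an intra-cluster correlation coefficient of 0.039 taken from ABA feasibility data", with about 12 women per IFH.
- Loss to follow-up: 5%.
- Not given: the share of outcome variance that intention explains. It is written R2 below and is an assumption throughout.

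**1. The protocol's own figures.** For two proportions with pooled variance, mean rate 0.475 and no continuity correction:

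n = [1.960 × √(2 × 0.475 × 0.525) + 1.2816 × √(0.44 × 0.56 + 0.51 × 0.49)]² / 0.07² = 1,067.4, rounded up to 1,068.

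This matches "a sample size of 2,136 women (1,068 per group) would be required". The design effect is 1 + 11 × 0.039 = 1.429, and 1,068 × 1.429 = 1,526. Dividing by 0.95 gives 1,606 + 1,124 = 2,730. The sample size reproduces with no covariate.

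**2. Power with intention in the model.** Let the covariate shrink only the individual-level variance, and leave the extra variance from IFH clustering untouched, which is the cautious choice:

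Var = 0.51 × 0.49 × [(1 − R2) + 11 × 0.039] / 1,526 + 0.44 × 0.56 × (1 − R2) / 1,068

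Power = Φ(0.07/√Var − 1.96)

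Worked case, R2 = 0.10: Var = 0.2499 × 1.329 / 1,526 + 0.2464 × 0.90 / 1,068 = 0.0002176 + 0.0002076 = 0.0004253. The SE is 0.02062, 0.07/SE = 3.394, and power = Φ(1.434) = 92.4%.

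| Assumed R2 | SE of risk difference (points) | SE relative to R2 = 0 | Power |
|---|---|---|---|
| 0 | 2.156 | 1.000 | 90.1% |
| 0.02 | 2.137 | 0.991 | 90.6% |
| 0.05 | 2.110 | 0.979 | 91.3% |
| 0.10 | 2.062 | 0.957 | 92.4% |
| 0.20 | 1.964 | 0.911 | 94.6% |
| 0.30 | 1.861 | 0.863 | 96.4% |

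Age and site are already in the planned model. R2 must therefore be read as what intention adds beyond them, which is less than its standalone value if intention tracks age or area.

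**3. Simulation check.** Each scenario had 300 runs, with 1,068 control women and 1,526 intervention women in clusters of 12, analysed by modified Poisson regression with cluster-robust SEs. Intention had three levels (60%, 20%, 20%). The control-arm rates below are assumed.

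| Rates by intention level | R2 | Mean SE of log RR, without → with | Mean RR, without / with |
|---|---|---|---|
| 52%, 38%, 26% | 0.045 | 0.0456 → 0.0446 | 1.155 / 1.155 |
| 58%, 32%, 14% | 0.132 | 0.0456 → 0.0426 | 1.164 / 1.163 |
| 65%, 22%, 3% | 0.283 | 0.0456 → 0.0388 | 1.157 / 1.157 |

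Simulated power went from 91% to 91%, 92% to 94%, and 90% to 97%. With 300 runs, each of these has a Monte Carlo SE of about √(0.91 × 0.09/300) = 1.7 points, so the SE column is the steadier guide. The risk ratio was built to be constant across intention levels, so its stability here does not show what happens when it varies.

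**4. Chance imbalance, illustrated.** Assume intention splits 50/50 with 8-week rates 50 points apart (R2 = 0.25 × 0.50² / 0.2464 ≈ 0.25). The SD of the between-arm difference in intention is √[0.25 × (1/1,526 + 1/1,068)] = 2.0 points. A 1-SD imbalance shifts the unadjusted estimate by 0.020 × 50 = 1 point, and a 2-SD imbalance by 2 points, against a 7-point target.

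**5. What adjustment estimates.** Take the middle scenario with a constant ratio of 51/44. The stratum differences are 58 × 7/44 = 9.2, 32 × 7/44 = 5.1 and 14 × 7/44 = 2.2 points. A constant ratio thus implies a varying difference. Section 13.2.1 reports both measures, so both should be averaged over the trial population.

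**The case against.** The planned analysis contradicts nothing in the protocol. Adjusting for the allocation variables and the IFH clustering is standard and valid, and step 1 shows adequate power on the protocol's own terms. This stands. A reader might infer that the primary analysis is biased or the trial underpowered; the documents support neither.

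Section 13.2 presents itself as an outline, and the SAP, which is not shown, may add covariates. That is possible. But section 13.2.1 names specific model terms, and a SAP that follows it would leave intention out.

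The strength of intention as a predictor is not documented. Section 13.3 lists it unranked beside education, deprivation and relationship status. A reader might take it to be a dominant predictor, but no figure in the protocol shows that. This stands, and is why the range starts at R2 = 0.02, where the gain is about half a power point.

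A reader might also assume that adjustment leaves the target effect unchanged because risk ratios are collapsible. The conditional ratio equals the marginal one only if it is constant across intention strata, which is what the subgroup interaction in section 13.3 will examine. Standardisation answers this, though it changes the estimation step as well as adding a term.

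An extra covariate may also make a log-binomial model with two random effects harder to fit. A fixed-effect log-binomial fit never failed in the simulations, but it had no random effects, so convergence of the planned model is untested.

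Finally, intention is not ignored: imbalance would be visible at baseline, and subgroup estimates are planned. Neither corrects the overall estimate.

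**Conclusion.** The point holds as lost precision and uncorrected chance imbalance in a valid analysis. The omission is on the face of section 13.2.1, and the protocol's own description of intention makes it a natural covariate.

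The size is uncertain. It runs from about half a power point at R2 = 0.02 to about six points at R2 = 0.30, with the SE falling by about 1% to 14%. This rests on an assumed increment beyond age and site, on the section 13.1 rates and intra-cluster correlation, and on adjustment leaving the IFH variance component unchanged. The R2 = 0 row also takes no credit for age and site, so the planned model may do slightly better than 90.1%. The change is worth making because the data are already collected, not because the primary result is at risk without it.

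**What to change.** Before any unblinded comparison, amend section 13.2.1 and the SAP:

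1. Add baseline feeding intention, with categories fixed in advance, as a fixed effect in the model for the primary outcome and the other breastfeeding outcomes.
2. Report the marginal risk ratio and risk difference by standardisation over the trial population, with confidence intervals that respect the IFH clustering.
3. Keep the treatment-by-intention interaction as a separate subgroup analysis, as planned.
4. Retain the Poisson model with robust variance as the fallback, with the same covariates.

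The same edit can settle two wording points in section 13.2.1. Age appears both as a group and as a continuous variable, and the minimisation variables are listed in section 6.3, not 6.2.

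The cost is wording and some programming for the standardisation. No new data, visits or participants are needed. The one technical downside is a possibly harder mixed log-binomial fit, which item 4 covers.

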## 13.2.2. Secondary Outcomes

The binary secondary outcomes (i.e. breastfeeding initiation; any breastfeeding at 16-weeks and 24-weeks post birth; exclusive breastfeeding at 8-, 16- and 24 weeks; and any infant hospital admissions at 16-weeks post birth) will be analysed using the same methods described for the primary outcome (section 15.2.1), and results presented as adjusted risk ratios, risk differences with corresponding 95% confidence intervals and p-values.

For those secondary outcomes that are continuous (e.g. if ceased breastfeeding, duration of any and exclusive breastfeeding; anxiety measured by the GAD-7 at 8-weeks and 16-weeks; health related quality of life measured by the EQ-5D-5L at 8 and 16-weeks; social support measured at 8- and 16-weeks; self-reported formula feeding practices at 8- and 16-weeks post birth), linear regression methods will be used if the outcome is sufficiently normally distributed (or where data can be suitably transformed), adjusting for the minimisation variables listed in section 6.2 and baseline measures where relevant, including IFH and site from minimisation variables as random effects, to calculate an adjusted mean difference with 95% confidence intervals and associated 2-sided p-values.

Maternal use of support for infant feeding at 8- and 16-weeks post birth; diagnosis of tongue tie in baby and whether treated, measured at 8-weeks post birth; and self-reported formula feeding practices (how formula is prepared) will be presented descriptively.

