### 8.2.2.1. Clinical

- Breastfeeding initiation defined as baby put to the breast, even if this was on one occasion only and includes giving babies expressed breast milk.
- $\circ$   $\,$  Any breastfeeding at 16-weeks post birth.
- Any breastfeeding at 24-weeks post birth.
- Exclusive breastfeeding at 16-weeks post birth (defined in accordance with the WHO definition of infants who received only breast milk during the previous 24 hours);
   "Exclusive breastfeeding is defined as the baby receiving no other food or drink, not even water, except breast milk (including milk expressed), but allows the infant to receive oral rehydration solution, drops and syrups (vitamins, minerals and medicines)."
- Exclusive breastfeeding at 24-weeks post birth.
- Time to cease exclusive feeding with breastmilk, up to 16-weeks.
- $\circ$  Time to cease feeding with any breastmilk, up to 16-weeks.
- Maternal anxiety at 8-weeks post birth (measured by the Generalised Anxiety Disorder Assessment (GAD-7))
- Maternal anxiety at 16-weeks post birth (measured by the GAD-7)
- Maternal health related quality of life at 8-weeks (measured by the EuroQol (EQ-5D-5L))
- Maternal health related quality of life at 16-weeks (measured by the EQ-5D-5L)
- Maternal social support at 8-weeks post birth (measured by Medical Outcomes Study (MOS) Emotional / Informational Support domain;)
- Maternal social support at 16-weeks post birth (measured by MOS Emotional / Informational Support domain;)
- The following maternal self-reported formula feeding practices (how formula is prepared) (using questions from the UK Infant Feeding Survey;) at 8-weeks post birth and 16-weeks post birth:
  - Making one feed at a time
  - Correct water temperature

- Adding formula powder before water
- $\circ$  Making up formula when needed when out of the home
- Keeping milk chilled when out of the home
- Making formula with hot water when out of the home
- Sterilising bottles using recommended methods
- Maternal use of support for infant feeding (e.g. national breastfeeding helpline; peer support; breastfeeding groups) at 8-weeks post birth and 16-weeks post birth.
- Diagnosis of tongue tie in baby and whether treated, measured at 8-weeks post birth.

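### Breastfeeding duration is compared by linear regression only in women who have stopped, so the two duration outcomes are not a randomised comparison and can be biased in either direction

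*Protocol*

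**What the plan says.** Protocol section 8.2.2.1 lists two duration outcomes: "Time to cease exclusive feeding with breastmilk, up to 16-weeks" and "Time to cease feeding with any breastmilk, up to 16-weeks". As worded, both are times to an event with a fixed horizon, and they have meaning for every woman followed.

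Section 13.2.2 handles them differently. Its paragraph on linear regression opens: "For those secondary outcomes that are continuous (e.g. if ceased breastfeeding, duration of any and exclusive breastfeeding". The stated result is an adjusted mean difference with a confidence interval and p-value. The only condition on the method is that the outcome be roughly normal or transformable.

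Section 13.2 commits all analyses in the first instance to intention to treat. Its only exclusion is for pregnancy loss, stillbirth or infant death before an assessment. No survival or other censored-data method appears anywhere in the protocol.

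**The concern.** The three sections do not fit together. A woman still feeding at 16 weeks has an observed value under section 8.2.2.1 (at least 16 weeks), belongs in the analysis under section 13.2, and is removed by section 13.2.2.

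She is removed because of something that happens after randomisation and that the intervention is designed to influence. If the intervention works, a different share is removed from each arm. A woman carried past 16 weeks leaves the intervention mean instead of raising it. The women who remain are not comparable between arms, and adjusting for age and site does not restore comparability. A check on normality does not deal with censoring either.

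At stake are two pre-specified secondary results with p-values, which could misstate the benefit or appear to conflict with the primary result.

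The exclusive-feeding outcome has a further ambiguity. If the condition refers to stopping any breastfeeding, mixed feeders whose exclusive feeding has a known end would also be dropped.

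**Working it through.** **Planning figures.** The protocol gives no figure for the duration outcomes, so its 8-week planning rates serve as the anchor: "Assuming 90% power and a 2-sided 5% significance level, with a control group rate of 44% for the primary outcome", rising to 51%. The sample size built on them reproduces. The pooled two-proportion formula gives 1,067.4, so 1,068 per group. The design effect is 1 + 11 × 0.039 = 1.429, and 1,068 × 1.429 = 1,526. Dividing by 0.95 gives 1,606 and 1,124, total 2,730. None of this is in dispute.

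**Assumptions.** The protocol gives no 16-week rate and no duration distribution. The assumed control curve S(t) for any breastfeeding is 75%, 60%, 52%, 44% and 36% at weeks 0, 2, 4, 8 and 16, log-linear between these points. Initiation is the same in both arms. The intervention multiplies the cessation hazard by a constant HR within a stated window and has no effect outside it, with HR set so that S(8) = 51%.

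**Formulas.**
- Restricted mean over all women: R = area under S(t) from 0 to 16.
- Mean among starters who stopped by week 16: M = (R − 16·S(16)) / (S(0) − S(16)).
- HR for an effect starting at week a and lasting at least to week 8: ln(0.51/S(a)) / ln(0.44/S(a)). From week 0 this is 0.723, from week 2 it is 0.524, from week 4 it is 0.116.
- S(16) if the effect ends by week 8: 0.51 × 0.36/0.44 = 0.417.

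**Control arm.** R = 7.57. M = (7.57 − 5.76)/(0.75 − 0.36) = 4.63 weeks. The share dropped as still feeding is 36%.

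**Intervention minus control, in weeks.** The last column counts never-initiators as zero-duration stoppers, so the denominator of M becomes 1 − S(16).

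| Effect window (weeks) | Still feeding at 16, intervention | Restricted-mean difference | Stopped-only difference, starters | Stopped-only, never-initiators at 0 |
|---|---|---|---|---|
| 0–2 | 42% | +1.09 | +1.32 | +0.58 |
| 0–4 | 42% | +1.01 | +1.09 | +0.44 |
| 0–8 | 42% | +0.90 | +0.74 | +0.24 |
| 2–8 | 42% | +0.76 | +0.33 | +0.01 |
| 4–8 | 42% | +0.65 | 0.00 | −0.18 |
| 0–16 (proportional hazards) | 44% | +1.00 | +0.24 | −0.13 |
| 2–16 | 46% | +0.94 | −0.65 | −0.68 |
| 4–16 | 50% | +0.99 | −2.32 | −1.66 |

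Straight-line interpolation changes the differences by at most 0.02.

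**Reading the table.** Every row has the same planned effect at week 8 and a genuine gain in feeding time. Among starters, the stopped-only estimate is too large in the first two rows, too small in the next four, and of the wrong sign in the last two. It also moves with how never-initiators are counted, which section 13.2.2 does not state.

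**Second check, different assumptions.** Five discrete patterns were tried with 30–38% of control still feeding at 16 weeks and 20–30% never starting or stopping in week 1. The stopped-only difference ran from −0.7 to +1.1 weeks, against restricted-mean gains of +0.6 to +1.2. Two patterns reversed sign, two understated the gain and one overstated it.

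**The case against.** The strongest reply concerns direction and weight.

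- **Direction.** A reader might infer that the analysis will usually show no effect or apparent harm. The documents do not support that. Section 7.1.2 ends support at 8 weeks after birth and puts the offered daily contact in the first 2 weeks. If the effect ends by week 8, no stopped-only difference among starters is negative, and two overstate the benefit. The −2.32 row needs an HR of about 0.12, so that intervention feeding falls only from 52% to 50% between weeks 4 and 16 while control falls from 52% to 36%. That is a 14-point gap at week 16, twice the planned 7 points.
- **Who is dropped.** It is tempting to say that the analysis removes the women who benefit most. Those removed include women carried past 16 weeks by the intervention, but on the assumed curve 36% of control women also feed that long. Most of those dropped would have continued anyway.
- **Exclusive feeding.** Fewer women may be affected here. Section 1.1 cites 12% exclusively breastfed in England at 4 months.
- **Status of the text.** Section 13.2 calls itself a brief outline and defers to an SAP that is not at hand, the linear model is conditional on distribution, and section 8.2.2.1 already uses time-to-event language.
- **Reach.** The primary outcome and any and exclusive breastfeeding at 16 and 24 weeks are binary and are not conditioned on stopping, so persistence is still tested on the randomised groups.

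The points on direction, on who is dropped and on reach stand, and they limit the finding. The point on status stands only in part: section 13.2.2 names the analysis set, the model and the effect measure. An SAP that follows it inherits the problem, and one that corrects it departs from the protocol.

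**Conclusion.** The point holds as a conflict between sections 8.2.2.1, 13.2 and 13.2.2, and as a method that does not preserve the randomised comparison. The adjusted mean difference can understate, overstate or, under some effect patterns, reverse the true effect.

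Among starters, on the assumed curve, the stopped-only difference is 0.0 to +1.3 weeks when the effect stops by week 8 (restricted-mean gain +0.65 to +1.1). When the effect persists to week 16, it is +0.24 under proportional hazards and negative if the effect begins only after week 2 (gain about +0.9 to +1.0). These sizes illustrate the problem and do not predict the result, because they rest on an assumed control curve and assumed effect windows. That reversal is possible is supported; that it is likely is not.

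The matter should be corrected before analysis, but it does not threaten the trial's main conclusion.

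**What to change.** Take duration of any and exclusive breastfeeding, with its condition on having stopped, out of the linear-regression list in section 13.2.2. In its place:

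- Analyse time from birth to cessation in all randomised women with an eligible live infant. Keep women still feeding in the analysis, censored at 16 weeks or at last known feeding status.
- Use a censored-data method, for example Cox regression or the difference in restricted mean time to 16 weeks. Adjust for age and site and account for clustering by infant feeding helper.
- State how women who never start are counted.
- State the event separately for any and for exclusive feeding, so that mixed feeders are not lost from the exclusive outcome.
- Confirm what is recorded. Table 1 lists only feeding status at day 3 and weeks 8, 16 and 24, and the protocol does not say whether a stopping date or age is asked. If only status is held, use an interval-censored version.

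The cost is a change of wording in the protocol and SAP and a little more analysis work. Whether the existing forms give exact stopping times cannot be confirmed from the protocol, but the interval-censored version works with the status data already planned.
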